16.6 Appendix 6: Sampson Criteria for Diagnosing Anaphylaxis

Anaphylaxis is highly likely when any one of the following three criteria is fulfilled:

1. Acute onset of an illness (minutes to several hours) with involvement of the skin, mucosal tissue, or both (eg, generalized hives, pruritus or flushing, swollen lips- tongue-uvula)

AND AT LEAST ONE OF THE FOLLOWING:

- a. Respiratory compromise (eg, dyspnea, wheeze-bronchospasm, stridor, reduced peak expiratory flow [PEF], hypoxemia)

- b. Reduced blood pressure or associated symptoms of end-organ dysfunction (eg, hypotonia [collapse], syncope, incontinence)

2. Two or more of the following that occur rapidly after exposure to a likely allergen for that patient (minutes to several hours):

- a. Involvement of the skin-mucosal tissue (eg, generalized hives, itch-flush, swollen lips-tongue-uvula)

- b. Respiratory compromise (eg, dyspnea, wheeze, bronchospasm, stridor, reduced PEF, hypoxemia)

- c. Reduced blood pressure or associated symptoms (eg, hypotonia [collapse], syncope, incontinence)

- d. Persistent gastrointestinal symptoms (eg, painful abdominal cramps, vomiting)

3. Reduced blood pressure after exposure to a known allergen for that patient (minutes to several hours):

- a. Infants and children: low systolic blood pressure (age specific) or >30% decrease in systolic blood pressure*

- b. Adults: SBP <90 mmHg or >30% decrease from that person's Day 1 reading

*Low SBP for children is age specific and defined as: <70 mmHg from age 1 month to 1 year; <70 mmHg + [2 x age] for age 1 to 10 years; <90 mmHg from age 11 to 17 years.

Source: Sampson et al 2005 and Sampson et al 2006

16.7 Appendix 7: Reference table blood volume by weight

Blood volume drawn for the purpose of this study is limited to a maximum of 2.5% of the circulating blood volume per sampling session and to a maximum of 5% over a 4-week period (Table 16-10) (Howie 2011). Investigators may further limit the volume of blood withdrawn based on local institutional guidelines and if the clinical condition of the participant may be adversely affected by removal of the blood volumes stated below. Details of blood volume requirement for [REDACTED] biomarker and safety samples are provided in the laboratory manual.

Table 16-10 Reference table – blood collection volumes by body weight

Body Weight (kg)	Total blood volume (TBV) of the participant (mL) ¹	Maximum allowable volume (mL) in one blood draw (2.5% of TBV)	Total maximum volume (mL) drawn in a 28-day period (5% of TBV)
20	1600	40	80
21	1680	42	84
22	1760	44	88
23	1840	46	92
24	1920	48	96
25	2000	50	100
26	2080	52	104
27	2160	54	108
28	2240	56	112
29	2320	58	116
30	2400	60	120
31	2480	62	124
32	2560	64	128
33	2640	66	132
34	2720	68	136
35	2800	70	140
36	2880	72	144
37	2960	74	148
38	3040	76	152
39	3120	78	156
40	3200	80	160
41	3280	82	164
42	3360	84	168
43	3440	86	172
44	3520	88	176
45	3600	90	180
46	3680	92	184
47	3760	94	188
48	3840	96	192
49	3920	98	196
50	4000	100	200
51	4080	102	204
52	4160	104	208

Body Weight (kg)	Total blood volume (TBV) of the participant (mL) ¹	Maximum allowable volume (mL) in one blood draw (2.5% of TBV)	Total maximum volume (mL) drawn in a 28-day period (5% of TBV)
53	4240	106	212
54	4320	108	216
55	4400	110	220
56	4480	112	224
57	4560	114	228
58	4640	116	232
59	4720	118	236
60	4800	120	240
61	4880	122	244
62	4960	124	248
63	5040	126	252
64	5120	128	256
65	5200	130	260
66	5280	132	264
67	5360	134	268
68	5440	136	272
69	5520	138	276
70	5600	140	280
71	5680	142	284
72	5760	144	288
73	5840	146	292
74	5920	148	296
75	6000	150	300
76	6080	152	304
77	6160	154	308
78	6240	156	312
79	6320	158	316
80	6400	160	320

1: Assuming a TBV of 80 mL per kg

For body weights not listed in the Table, use the following formulas to calculate 2.5% and 5% of total blood volume:

- **2.5% of total blood volume = body weight (in kg to the closest 0.5 kg) X 2**
- **5% of total blood volume = body weight (in kg to the closest 0.5 kg) X 4**

ALP	Alkaline phosphatase
ALT	Alanine aminotransferase
Apo A1	Apolipoprotein A1
Apo B	Apolipoprotein B
AST	Aspartate aminotransferase
ATC	Anatomical Therapeutic Chemical
BMI	Body Mass Index
[REDACTED]	[REDACTED]
CRF	Case Report/Record Form (paper or electronic)
CRO	Contract Research Organization
DBP	Diastolic Blood Pressure
DMC	Data Monitoring Committee
ECG	Electrocardiogram
eGFR	Estimated glomerular filtration rate
EudraCT	European Union Drug Regulating Authorities Clinical Trials
FAS	Full Analysis Set
FH	Familial Hypercholesterolemia
HbA1c	Hemoglobin A1c
HDL-C	High density lipoprotein cholesterol
HoFH	Homozygous Familial Hypercholesterolemia
ISR	Injection site reaction
LDL	Low density lipoprotein
LDL-C	Low density lipoprotein cholesterol
LFT(s)	Liver function test(s)
LLOQ	Lower limit of quantification
Lp(a)	Lipoprotein (a)
MMRM	Mixed-effect model for repeated measures
OAS	Open-label Phase Analysis Set
PCSK9	Proprotein convertase subtilisin/kexin type 9
PT	Preferred term
s.c.	Subcutaneous
SAE	Serious adverse event
SAF	Safety analysis set
SAP	Statistical Analysis Plan
SBP	Systolic Blood Pressure
SCR	Screened set
SD	Standard deviation
SOC	System Organ Class

Novartis
SAP amendment 4

For business use only

Page 11
CKJX839C12302

TEAE	Treatment emergent adverse event
ULN	Upper limit of normal
WBC	White blood cell(s)

1 Introduction

This document contains details of the statistical methods that will be used in the Phase 3 clinical trial CKJX839C12302 (ORION-13). The purpose of this Phase 3 study is to evaluate safety, tolerability, and efficacy of inclisiran in adolescents (aged 12 to <18 years) with homozygous familial hypercholesterolemia HoFH and elevated LDL-C (LDL-C >130 mg/dL (3.4 mmol/L)). The use of inclisiran (as an adjunct to stable, optimal background lipid-lowering therapy) for the treatment of HoFH in adolescent patients who require additional lipid-lowering will be investigated to obtain needed pediatric information on inclisiran. Percentage change in LDL-C from baseline to Day 330 (Year 1) is the primary endpoint of this study.

The analysis plan has been prepared based on the ORION-13 study protocol version V02 (protocol amendment 2), content final dated 17-Feb-2023.

Important information is given in the following sections and details are provided, as applicable, in [Section 5](#).

[figure not shown]
1.1 Study design

This study is a two-part (double-blind, placebo-controlled / open-label) multicenter study in adolescents (aged 12 to <18 years) with HoFH and elevated LDL-C (>130 mg/dL / 3.4 mmol/L) on stable, individualized, optimal SoC background lipid-lowering therapy (including maximally tolerated statin treatment). The overall study duration is 748 days.

Following an approximately 4 weeks screening/run-in period, the study has two sequential parts ([Figure 1-1](#)).

- **Part 1 (Year 1):** 12 months double-blind, parallel group period in which participants will be randomized to receive either inclisiran sodium 300 mg (equivalent to 284 mg inclisiran) s.c. or placebo (given at Days 1, 90 and 270).
- **Part 2 (Year 2):** 12 months single arm, open-label follow-up period with all participants receiving inclisiran sodium 300 mg s.c. Participants randomized to placebo in Part 1 will receive inclisiran starting on Day 360 (“Switch” Day 360). Participants randomized to inclisiran in Part 1 will receive placebo on Day 360. This dose of inclisiran/placebo on Day 360 will remain blinded to maintain the blind for Part 1 of the study. All participants will receive subsequent doses of open label inclisiran on Days 450 and 630.

Approximately 12 participants who meet the inclusion/exclusion criteria were to be randomized in a 2:1 ratio to receive either inclisiran sodium 300 mg s.c. or placebo on Day 1 (baseline). Information regarding sample size calculation is provided in [Section 3](#).

Figure 1-1 Study design

* Primary endpoint assessed at Day 330. # "Switch Day": Participants randomized to placebo in Part 1 will start to receive inclisiran on Day 360. Participants randomized to inclisiran in Part 1 will receive placebo on Day 360 only to maintain the blind for Part 1.

The primary endpoint will be measured at Day 330.

1.2 Study objectives and endpoints

Section 2 of the study protocol lists the following primary, secondary, [REDACTED] objectives.

Table 1-1 Objectives and related endpoints

Objective(s)	Endpoint(s)
Primary objective(s)	Endpoint(s) for primary objective(s)

 The primary objective is to evaluate the effect of inclisiran compared to placebo on reducing LDL-C [percent change] at Day 330 (Year 1) in adolescents (aged 12 to <18 years) with HoFH and elevated LDL-C 	
 Percentage change in LDL-C from baseline to Day 330 (Year 1)
Secondary objective(s)	Endpoint(s) for secondary objective(s)

 Evaluate the effect of inclisiran compared to placebo on reducing LDL-C [time-adjusted percent change] over Year 1 Evaluate the effect of inclisiran compared to placebo (for Year 1) and 	
 Time-adjusted percent change in LDL-C from baseline after Day 90 and up to Day 330 (Year 1) Percent change and absolute change in LDL-C, Apo B, lipoprotein (a) [Lp(a)], non-high density

Novartis SAP amendment 4	For business use only	Page 14 CKJX839C12302
-----------------------------	-----------------------	--------------------------

Objective(s)	Endpoint(s)
long-term (up to Day 720), on lowering LDL-C, other lipoprotein and lipid parameters, and PCSK9 over time • Evaluate the safety and tolerability of inclisiran compared to placebo (for Year 1) and long-term (up to Day 720), in adolescents (aged 12 to <18 years) with HoFH	lipoprotein cholesterol (non-HDL-C), total cholesterol, triglycerides, HDL-C, very low density lipoprotein cholesterol (VLDL-C), apolipoprotein A1 (Apo A1) and PCSK9 from baseline to each assessment time up to Day 720 (Year 2) • Incidence, severity and relationship to study drug of treatment-emergent AEs and SAEs; vital signs; laboratory parameters; anti-drug antibodies (ADA) measurement; growth (height, weight, BMI); pubertal development (steroid hormones and Tanner staging)

2 Statistical methods

2.1 Data analysis general information

All analyses will be performed by Novartis. The most recent version of SAS available in the statistical programming environment of Novartis will be used for the analysis.

Part 1 data are defined as all data collected starting from screening visit up to the day 360 visit date prior to dosing day/date. Part 1 data will be presented by two separate groups (inclisiran

and placebo). The total column will be presented in all outputs of Part 1 as needed and will be specified in TFL shell document.

Part 2 data are defined as all data collected starting from after dosing on day 360. Part 2 data will be presented in two separate groups, (1) inclisiran since Day 1 and (2) placebo-to-inclisiran, unless otherwise specified. The column labels for these two groups will be inclisiran-inclisiran and placebo-inclisiran. The total column will be presented in all outputs of Part 2 as needed and will be specified in TFL shell document.

For instances, where it will not be possible to distinguish whether data belong to Part 1 or Part 2, based on the dosing time on the day 360 visit, all data collected from screening up to the day 360 visit will be considered as Part 1 data and all data captured after the day 360 visit (starting from day 360 visit + 1 day) will be considered as Part 2.

Part 1 data analysis will be performed after all participants completed the day 360 visit (Part 1) or discontinued the study prior to the Day 360 visit. For each participant data, collected in the database till the end of study Part 1 (up-to Day 360 visit as mentioned above) will be included in this analysis. Hence Day 360 visit of a participant will serve as data cut-off date for that participant. All events with start date before or on the cut-off date and for which the end date has not been reached yet or they are ongoing at final visit will be reported as 'ongoing'. The same rule will be applied to events starting before or on the cut-off date and not having a documented end date. The assessment of study primary objective and key secondary objectives will be based on this analysis.

Part 2 analysis will be conducted after all participants either completed the study or discontinued early.

Both Part 1 and Part 2 analyses will be reported in CSR. For summary of the analyses that will be performed for Part 1 analysis and Part 2 analysis see [Appendix 5.3](#).

Detailed information regarding DMC analysis will be provided in the DMC charter and a separate DMC SAP/TFL shells.

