4.5 Risks and benefits

It is widely recognized that LDL-C plays a major role in the initiation and progression of ASCVD, including in HoFH, and accumulated exposure of elevated LDL-C is causally related to the development of ASCVD. As the degree and duration of exposure to elevated LDL-C levels increases the atherosclerotic burden, early treatment of HoFH is vital. Published expert guidelines recommend a LDL-C target of ≤ 130 mg/dL in children/adolescents. Current treatment options to achieve these targets are still limited for children with FH and the well-known limitations of contemporary therapies are particularly relevant among pediatric patients with FH. Furthermore, even at the highest doses of the most efficacious statins, only modest reductions in LDL-C plasma levels of 10%-25% are observed in most patients with HoFH.

In adult studies in participants with ASCVD, ASCVD risk equivalents, and/or HeFH, inclisiran given on Day 1, Day 90 and every 6 month thereafter lowered LDL-C by ~50% versus placebo in participants on maximally tolerated statin therapy \pm other lipid-lowering therapies. The effect was persistent over time and reversible on stopping inclisiran.

In non-clinical toxicity studies, inclisiran was not carcinogenic or genotoxic, there was no effect on paternal performance, spermatogenesis, estrous cycle, and uterine or ovarian parameters and inclisiran did not show evidence of embryolethality, fetotoxicity, or teratogenicity. In addition, there were no effects of inclisiran on the development of the F1 generation, including survival, growth, physical and reflexological development, behavior, and reproductive performance. The safety profile of inclisiran in clinical studies was generally comparable to placebo. The only Adverse drug reaction (ADR) identified in clinical studies was a higher incidence of TEAEs at the injection site with inclisiran (preferred terms of injection site erythema, injection site hypersensitivity, injection site pruritus, injection site rash, and injection site reaction). However, all TEAEs at the injection site were localized, were predominantly mild or occasionally moderate, transient, and resolved without sequelae. The impact of this side effect is further mitigated by the infrequent dosing regimen of inclisiran.

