6.1.1 Investigational and control drugs

The sponsor will provide the following investigational and control drugs as single-use pre-filled syringes for s.c. injection ([Table 6-1](#)).

Part 1 (Year 1) including “Switch” Day 360:

- Inclisiran sodium 300 mg (equivalent to 284 mg inclisiran) in 1.5 mL solution
- Placebo formulation to this active drug formulation

Placebo will be supplied as sterile normal saline (0.9% sodium chloride in water for injection). Placebo will be administered as a 1.5 mL s.c. injection to match the dose in the inclisiran arm.

The placebo pre-filled syringes will be blinded and look identical to the corresponding inclisiran pre-filled syringes.

Part 2 (Year 2):

- Inclisiran sodium 300 mg (equivalent to 284 mg inclisiran) in 1.5 mL solution

Table 6-1 Investigational and control drug

Investigational/ Control Drug	Pharmaceutical Dosage Form	Route of Administration	Supply Type	Sponsor (global or local)
Inclisiran sodium 300 mg (equivalent to 284 mg inclisiran*) in 1.5 mL solution	Solution for injection	Subcutaneous injection	Solution for injection in pre-filled syringe	Sponsor (global)
Placebo	Solution for injection	Subcutaneous injection	Solution for injection in pre-filled syringe	Sponsor (global)

* Inclisiran is also referred to as KJX839

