For occurrence, the presence of at least one SAE / SAE suspected to be related to study treatment / non-SAE has to be checked in a block e.g., among AEs in a ≤ 1 day gap block, if at least one SAE is occurring, then one occurrence is calculated for that SAE.

The number of deaths resulting from SAEs suspected to be related to study treatment and SAEs irrespective of study treatment relationship will be provided by SOC and PT.

These summaries will be provided after full study completion.

Injection site reactions

The number and percentage of participants who reported injection site reaction TEAEs will be summarized in the following ways:

- SOC, PT, treatment group and Part.
- SOC, PT, severity, treatment group and Part.

Listing will be provided for participants with injection site reactions.

The time to the first injection site reaction will also be summarized by treatment and Part using the following categories: $\leq 4h$, $4h$ to $\leq 12h$, $>12h$. The time (hours) to the event will be calculated from the most recent administration of study drug. The duration of the first and the longest injection site reaction will be summarized by treatment and Part using descriptive statistics. The outcome of the first and the longest injection site reaction will be summarized using the following categories: Resolved ($\leq 4h$, $>4h$ to ≤ 7 days, >7 days to ≤ 14 days, >14 days), not resolved and unknown. The total number of injection site reactions per participants will be summarized in categories (e.g., 1, 2, 3, and >3 etc.). Symptoms of injection site reactions will be summarized by treatment group and Part.

Other safety topics

The number and percentage of participants who reported TEAEs of other safety topics will be summarized by PT, treatment group and Part. PTs will be sorted in descending order of frequency in the total column. If a participant reported more than one AE within the same PT, the AE will be counted only once. If a participant reported more than one AE within the same safety topic, the participant will be counted only once at that safety topic. Listings of participants with AEs of other safety topics will be provided.

The Compound Case Retrieval Strategy (CRS) will be used to determine the MedDRA search criteria to be used to identify events of other safety topics.

AEs of other safety topics will include the following:

- Hepatic events
- Renal events
- Hypersensitivity events
- Neurological events
- Psychiatric events

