2.11 Interim analysis

Interim analyses are planned for the monitoring of participants' safety and will be performed as determined by the DMC (see DMC charter). Interim safety analyses before the unblinding for the analysis of Part 1 of the study will be performed by an independent statistician/programmer who will not be involved in the trial conduct. The interim results will be reviewed by the independent DMC.

3 Sample size calculation

The sample size for this study was selected based on feasibility.

4 Change to protocol specified analyses

No change from protocol specified analysis was made.

5 Appendix

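### The SAP's Part 2 injection site reaction tables put reactions to the blinded Day 360 saline in the inclisiran-inclisiran column and do not separate Day 360 from Days 450 and 630

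*SAP*

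**What the plan says.** - **Day 360.** SAP 1.1: "Participants randomized to inclisiran in Part 1 will receive placebo on Day 360". Participants randomised to placebo receive inclisiran that day, and both injections are blinded. Everyone then has open-label inclisiran on Days 450 and 630. Protocol 6.1.1 on the placebo: "Placebo will be supplied as sterile normal saline (0.9% sodium chloride in water for injection".
- **Start of Part 2.** SAP 2.1 begins Part 2 data after the Day 360 dose. SAP 2.7 makes an adverse event treatment-emergent in Part 2 if it starts after the Day 360 dosing time.
- **Part 2 columns.** SAP 2.1: "Part 2 data will be presented in two separate groups, (1) inclisiran since Day 1 and (2) placebo-to-inclisiran". The labels are inclisiran-inclisiran and placebo-inclisiran. The sentence goes on to allow for exceptions specified elsewhere, and SAP 2.1 leaves some column detail to the table shells.
- **ISR tables.** SAP 2.7.1: "The number and percentage of participants who reported injection site reaction TEAEs will be summarized in the following ways". The layouts are by system organ class, preferred term and (in one table) severity, each by treatment group and Part. Time to first ISR, duration and symptoms are also by treatment and Part. No grouping is stated for outcome or for the number of ISRs per participant. On timing: "The time (hours) to the event will be calculated from the most recent administration of study drug". Protocol 6.6.1 counts placebo as study drug, so a saline injection can start this clock.
- **Known reaction.** Protocol 4.5: "The only Adverse drug reaction (ADR) identified in clinical studies was a higher incidence of TEAEs at the injection site with inclisiran".

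**The concern.** A local reaction at the injection site belongs to the product injected there. A column defined by treatment sequence and Part cannot show which product that was. For the arm on inclisiran from Day 1, a reaction to the Day 360 saline would be read as a reaction to inclisiran, and its onset time and duration would be summarised with those of inclisiran reactions.

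The two Part 2 columns also differ in the number of active injections. A lower ISR percentage in the inclisiran-inclisiran column could be read as better local tolerance after longer exposure, when it may only reflect fewer active injections. Injection site events are the one adverse drug reaction the protocol identifies, and long-term tolerability is a secondary objective, so these tables will be read closely.

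**Working it through.** **No planned figure to reproduce.** The SAP gives no power or precision calculation: "The sample size for this study was selected based on feasibility" (SAP section 3). The check is a count of injections plus a labelled illustration.

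**Inputs from the documents.** "Approximately 12 participants who meet the inclusion/exclusion criteria were to be randomized in a 2:1 ratio" (SAP 1.1) gives 8 and 4 if exactly 12 are randomised. The Part 2 injection days are 360, 450 and 630.

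**Count for Part 2, all doses given**

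| Part 2 column | Participants | Injections | Saline | Inclisiran | Active per person |
|---|---|---|---|---|---|
| inclisiran-inclisiran | 8 | 8 × 3 = 24 | 8 | 16 | 2 |
| placebo-inclisiran | 4 | 4 × 3 = 12 | 0 | 12 | 3 |
| Total | 12 | 36 | 8 | 28 | |

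The saline share is 8/24 = 33% in the first column, 0/12 in the second and 8/36 = 22% overall. The one-third share does not depend on group size. It changes only if Part 2 doses are missed. The Open-label Phase Analysis Set (SAP 2.2) needs only one Part 2 dose of study treatment, so a participant whose sole Part 2 injection is the Day 360 saline still counts in the inclisiran-inclisiran denominator.

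**Effect on the percentages.** Reaction risks per injection are not in the documents. Assume p for inclisiran, s for saline, and independent injections.

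- inclisiran-inclisiran: P(at least one ISR) = 1 − (1 − s)(1 − p)²
- placebo-inclisiran: P(at least one ISR) = 1 − (1 − p)³

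| p | s | inclisiran-inclisiran | placebo-inclisiran |
|---|---|---|---|
| 5% | 0–5% | 10–14% | 14% |
| 10% | 0–5% | 19–23% | 27% |
| 20% | 0–5% | 36–39% | 49% |
| 30% | 0–5% | 51–53% | 66% |

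For p = 10%: 1 − 0.81 = 0.19 at s = 0; 1 − 0.95 × 0.81 = 0.23 at s = 5%; and 1 − 0.729 = 0.27. The gap comes from two against three active injections and closes only when s = p.

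**Number of saline reactors to expect.** At s = 2–5%, 8 × s = 0.16 to 0.40. The chance of none is 0.98⁸ = 85% down to 0.95⁸ = 66%. A participant who reacts to saline and to neither later injection would add 1/8 = 12.5 percentage points to the column.

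**What the Day 360 comparison can bear.** It sets 8 saline against 4 inclisiran injections. With no reactions in 8 saline injections, the exact 95% upper limit is 1 − 0.025^(1/8) = 37%. Fisher's two-sided p against 0/8 is 0.33 for 1/4 and 0.09 for 2/4. Only a descriptive display is warranted.

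**The case against.** The case for leaving the plan alone has substance.

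- **The effect is small and traceable.** The likeliest outcome is no saline reactor at all. Listings of adverse events and of participants with ISRs are planned, and SAP 1.1 states the Day 360 placebo openly. With about 12 participants, a reader can attribute each case by date. This stands and limits the weight of the point, but a listing does not correct the summary percentage.
- **The column is a sequence label.** Protocol 4.2 says the LDL-C effect lasts more than six months after a single dose. The label is therefore fair for efficacy and for most systemic events. The point is confined to reactions tied to the injection.
- **The shells may deal with it.** SAP 2.1 allows exceptions and refers to shells that were not available. The ISR text in SAP 2.7.1 is detailed and names no split by product or visit.

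Two stronger readings are tempting and are not supported.

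- **That the Day 360 contrast is shown nowhere.** Vital signs are repeated four hours after that injection (Protocol 6.7.2) and summarised by visit, time-point and group (SAP 2.7.5). Numbers dosed and injection location are shown by visit and group (SAP 2.4.1). The gap is in the adverse event and ISR tables only.
- **That randomised, blinded information is being wasted and pooling by product would buy real precision.** Any such gain comes from treating repeated injections in the same 12 people as independent, although under the planned schedule both arms contribute to both products. On Day 360 the groups also differ in prior exposure (three inclisiran against three placebo injections), so that day is not a clean repeat of the randomised comparison.

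**Conclusion.** The concern holds for ISRs with a recorded time. No adverse event or ISR table named in the SAP separates the blinded Day 360 injection from the open-label injections on Days 450 and 630. Reactions to saline are therefore counted under inclisiran-inclisiran, where a third of the planned injections (8 of 24) are saline, against none of 12 in the other column. With two against three active injections per participant, the Part 2 ISR percentages of the two columns should not be compared.

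This rests on the planned 8:4 split with every dose given, on the SAP text without the shells, and, for the illustrated percentages only, on assumed reaction risks and independence. For a Day 360 event without a time, SAP 2.1 and SAP 2.7 point to different Parts and need reconciling. That is a separate matter.

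The primary endpoint and the Part 1 comparison are unaffected for timed events. The expected distortion is small, but the correction is cheap and concerns the one identified adverse drug reaction, so it is worth making.

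**What to change.** In SAP 2.7.1, add an ISR table by the product actually given at the most recent injection and by dosing visit, with the number of injections as denominator and both events and participants shown. In the Part 2 ISR tables, put reactions to the Day 360 saline in their own row, outside the inclisiran count.

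Present this descriptively, with two notes: injections within a participant are correlated, and the Day 360 groups differ in prior exposure. If the shells already contain such a split, a cross-reference in SAP 2.7.1 is enough.

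The cost is one extra table or row with small counts, built from dosing and ISR data already collected. Trial conduct does not change.
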